5.2 Treatment Regimen

Study drug group- rhDNase I, 1mg/ml (0.1%) eye drops will be applied to both eyes q.i.d for 8 weeks. Control group – Vehicle eye drops will be applied to both eyes q.i.d for 8 weeks. For either group, the subject will be instructed to instill the first dose of the study medication in the morning at approximately 8 a.m., and then the remaining doses at approximately 4 hourly intervals. Therefore, doses will be scheduled at approximately 8 a.m., 12 noon, 4 p.m. and 8 p.m.

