6.5 Study Assessments

The following detailed procedures are performed at the designated clinic visit. All results will be documented on the subject's medical/research charts, source documents, and CRFs as required. All ophthalmic procedures will be performed on both eyes.

6.5.1 Visit 1 Screening Day -18 to 0

After obtaining informed consent, the following assessments will be performed within fourteen days prior to the subject receiving the first dose of study medication:

- Demographic information including: birth date, gender, race or ethnic origin.
- Medical History including prior medication use and prior procedures: Medical history will be
 obtained by interviewing the subject and will include a history of systemic (acute or chronic)
 GVHD, stem cell transplant history (including the date and type of transplant, degree of
 mismatch, if any, etc.), allergic history (including medications and food), substance abuse history

RhDNase treatment for ocular GVHD Version: 10.0; 07-26-2018

Page 29 of 47

(including alcohol) and a history of medication use (including prescription, OTC, and herbal products) during the past 30 days will also be completed.

- Ophthalmic history including: date when the oGVHD began, verification that the subject has had definite oGVHD, medications used by the subject to treat oGVHD, previous procedures to treat oGVHD. Ocular symptoms due to oGVHD will be quantified using the Ocular Surface Disease Index (OSDI) questionnaire (section 3.3.2).
- Ophthalmic Examination (slit lamp examination, Ocular Surface Redness Score, Fluorescein and Lissamine Dye staining, and a Schirmer 1 test)
- Pregnancy test (urine), if applicable. Women of reproductive age will be asked to use a method
 of birth control that is acceptable to the subject and the study doctor. This may include oral
 contraceptive pills, birth control implants/shots or patches, barrier methods or abstinence.
 Women of reproductive age will not be included in the study if they refuse to use any birth
 control measure, including abstinence.

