7.1 Sample Size Determination

The sample size is based on the primary efficacy end point (corneal RBS score) using the following assumptions: (i) mean RBS score in ocular GVHD population = 3.1, (ii) sigma (standard deviation) = 2.5, (iii) expected mean based on 60% effect = 1.24. These assumptions are based on our preliminary data in ocular GVHD patients where we found that treatment with DNase I eye drops reduced RBS score by 80% (mean).²⁵ A total of 30 subjects in each group will be required to detect the difference between groups using a 2-sided two-sample t test with an alpha level of 0.05 and 80% power. We elected to enroll 36 subjects per group.

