7.2 Statistical Methods

Biostatisticians from the Design and Analysis Core (DAC) of UIC-CCTS will perform the analysis. We will assess treatment efficacy based on the intent-to-treat principle using each participant's randomized treatment assignment to define treatment groups and outcomes. Safety variables will be analyzed with regard to treatment that participants actually received (the safety population). One eye (target eye) will be selected at screening visit for statistical comparisons as follows: (i) if only 1 eye meets inclusion criteria, this eye is used; (ii) if both eyes meet inclusion criteria, the eye with the higher RBS score is used; (iii) if both eyes have the same RBS score, then the one with the lower Schirmer I score is used; (iv) if both eyes have same scores, the right eye is used. Secondary analyses will be performed for the non-target eye as well. To assess the effect of treatment, we will compare each outcome measure between rhDNase I (study) vs. Vehicle (control) group over time using general linear mixed model, mixed-effects ordinal logistic regression, and mixed-effects multinomial logistic regression for continuous, ordinal and nominal variables respectively. Treatment, time and their interaction will be included in the model. Missing values of less than 25% will be imputed by using multiple imputations; otherwise will not be included in the analysis. Descriptive statistics will be utilized before the modeling to describe the sample. Assumptions behind each statistical method will be examined. Two-sided Pvalue less than 0.05 would be considered as statistical significance. All the analyses will be conducted by using SAS 9.2 (SAS Inst., Cary, NC).

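### The secondary non-target-eye analysis is not limited to eyes that met entry, so it can be diluted; analysing the eyes apart also forgoes a more precise secondary estimate

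*Combined protocol and SAP*

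**What the plan says.** Section 7.2 (Statistical Methods) picks a target eye at screening. Its first rule reads "if only 1 eye meets inclusion criteria, this eye is used". If both eyes qualify, the eye with the higher RBS score is taken, then the one with the lower Schirmer value, then the right eye. The section continues: "Secondary analyses will be performed for the non-target eye as well". The synopsis (Statistical Methodology) carries the same sentence.

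The model terms named are treatment, time and their interaction. No eye term, between-eye correlation or joint two-eye model is mentioned. Section 7.3 defines the analysis population by subject (treatment received and week 2 attendance), so it does not filter eyes.

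The two entry criteria in section 4.1 that can differ between eyes are Schirmer I below 10 and corneal/conjunctival staining of at least 1.

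Both eyes receive the assigned treatment: section 5.2 says "eye drops will be applied to both eyes q.i.d for 8 weeks". Both are examined: section 6.5 says "All ophthalmic procedures will be performed on both eyes".

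**The concern.** There are two separate issues.

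1. **Which eyes are in the set.** The first target-eye rule exists because the plan foresees subjects with a single qualifying eye. In each of them the non-target eye failed on Schirmer or staining, and nothing in 7.2 or 7.3 removes it. If such an eye has little or no staining to lose, it pulls the treatment difference toward zero, and an effective drug could seem not to work in the fellow eye. The clearance endpoint (section 3.3, item 3) is counted in eyes with no stated baseline requirement, so an eye with no corneal staining at entry could count as cleared in either arm.

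2. **Eyes analysed apart.** The trial treats and measures two eyes per subject, then reports a target-eye result and a separate, correlated fellow-eye result. A single model of the qualifying eyes could give a more precise secondary estimate from the same data.

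**Working it through.** **Inputs (section 7.1).** "mean RBS score in ocular GVHD population = 3.1"; "sigma (standard deviation) = 2.5"; "expected mean based on 60% effect = 1.24"; "2-sided two-sample t test with an alpha level of 0.05 and 80% power"; 30 per group required, 36 enrolled. The difference is 3.1 − 1.24 = 1.86.

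**Assumed, because the documents do not give them:**
- f, the share of subjects with one qualifying eye;
- g, the fraction of the effect that a non-qualifying eye keeps;
- ρ, the between-eye correlation.

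**Step 1: the plan's own figure.** Power is that of the two-sided two-sample t test (noncentral t), with 2n − 2 degrees of freedom and noncentrality δ / (SD × √(2/n)).
- n = 30: noncentrality 1.86 / (2.5 × √(2/30)) = 2.88, power 80.9%. At n = 29 power is 79.5%, so 30 per group reproduces.
- n = 36: noncentrality 3.16, power 87.6%. This is the one-eye reference.

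**Step 2: dilution of the non-target-eye analysis.** With n = 36 and SD 2.5, the diluted difference is 1.86 × (1 − f(1 − g)).

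| f | Difference, g = 0 | Power, g = 0 | Difference, g = 0.5 | Power, g = 0.5 |
|---|---|---|---|---|
| 0% | 1.86 | 87.6% | 1.86 | 87.6% |
| 10% | 1.67 | 80.0% | 1.77 | 84.1% |
| 20% | 1.49 | 70.2% | 1.67 | 80.0% |
| 30% | 1.30 | 58.7% | 1.58 | 75.4% |

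If non-responding eyes all sit at a score of zero, the SD shrinks too, and power is 80.8%, 72.7% and 63.8% for f = 10%, 20% and 30%.

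**Step 3: what simple restriction would cost.** Keeping only qualifying fellow eyes holds the difference at 1.86 but leaves about 36 × (1 − f) = 32, 29 or 25 per group. Power is then 83.4%, 79.5% and 73.2%. That beats keeping all eyes when g = 0, but not when g = 0.5.

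**Step 4: joint model of qualifying eyes.** The mean of two eyes with equal SD has variance SD² × (1 + ρ)/2. Take n = 36 per group. For the column with half the subjects bilateral, information per subject relative to one eye is 0.5 + 0.5 × 2/(1 + ρ). In the last column the fellow-eye effect is 80% of the target's (assumed) and the SD is the same, so the unweighted mean effect is 0.9 × 1.86 = 1.67.

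| ρ | Variance ratio | Power, all bilateral, equal effects | Power, half bilateral, equal effects | Power, all bilateral, fellow effect 80% |
|---|---|---|---|---|
| 0.5 | 0.75 | 94.9% | 92.0% | 90% |
| 0.7 | 0.85 | 92.2% | 90.1% | 86% |
| 0.9 | 0.95 | 89.1% | 88.4% | 82% |

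With equal effects and all subjects bilateral, the standard error falls by 13%, 8% and 3%. In the last column the gain over the target eye alone (87.6%) is gone by ρ = 0.7. A fellow-eye-only analysis in that setting has difference 0.8 × 1.86 = 1.49 and power 70.2%, so the joint model still does better than the analysis it would replace.

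**The case against.** A reader might infer that the non-target analysis does contain ineligible eyes and is diluted. The documents do not support that as fact. The first target-eye rule is conditional, no share of one-eye subjects is given, and at a share of zero there is no dilution. Nor must a non-qualifying eye be unable to improve: it can fail on Schirmer alone and still stain. The 59% figure needs both a 30% share and no response in those eyes.

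A reader might also infer that precision is certainly being lost against the target-eye analysis. When both eyes qualify, the target is the eye with the higher RBS score, and the planned effect is proportional (60%), so the fellow eye may show a smaller absolute change. Step 4 shows that this can cancel the gain.

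Other objections have force. The average effect over all treated fellow eyes is a legitimate quantity in a randomised comparison, not a biased one. The values 1.86 and 2.5 were set for the corneal RBS score in the primary comparison, whereas the endpoint in section 3.2 is fluorescein and lissamine staining, so the power figures illustrate scale and do not predict the fellow-eye analysis. A joint model contains the target eye, so it gives no independent fellow-eye replication. Filtering on entry criteria does not remove every eye at the floor, because an eye can qualify on conjunctival staining and have no corneal staining to clear.

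These points limit the size of the concern. They do not answer the omission: the plan foresees single-qualifying-eye subjects and does not say how their other eye is handled in an efficacy analysis.

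**Conclusion.** The point holds in conditional form, as an inexpensive improvement to a secondary analysis. The non-target set can include eyes that failed entry, and nothing in 7.2 or 7.3 excludes them. The loss ranges from none to a fall in power from 87.6% to 58.7%, over assumed shares of 0–30% and with those eyes keeping between none and half of the effect.

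The joint analysis offers 95–89% power for ρ of 0.5–0.9 if both eyes of every subject qualify and respond equally. That advantage over the target eye is not assured. Against the fellow-eye-only analysis it was better in the unequal-effect case worked above (82–90% against 70%). All of this rests on planning values set for another comparison and on assumed f, g and ρ. The primary target-eye comparison and its sample size are not touched.

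**What to change.** Keep the target eye as primary. In section 7.2, and in the matching synopsis sentence, replace the non-target-eye statement with wording such as:

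*The main eye-level secondary analysis will include all eyes that met the eye-level entry criteria at screening, in one mixed model with a subject random effect (eye within subject), the eye's baseline score and a target/fellow eye term. Results for all non-target eyes, including those that did not meet the criteria, will be reported descriptively.*

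This takes one sentence in two places and no new data, and every subject stays in through the target eye. It should be settled before unblinding, so that the choice of eyes cannot follow the results.

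The plan should state the downsides: the joint estimate averages over eyes whose effects may differ, and it does not replicate the target-eye result independently. Eyes that qualified on conjunctival staining alone may still have no corneal staining to clear, and the baseline score in the model addresses this only in part.

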The most likely discomforts a subject may experience by using rhDNase I administered as eye drops are eye burning or irritation, red watery eyes, or feeling like there is something in the eye. To see how subjects react to the study medication, their first dose will be given by the investigator in the clinic itself. Afterwards subjects will be asked to rate tolerability of the drug on the Visual Analogue Scale. Also, at each visit, subjects will be asked to complete the Visual Analogue Scale.

An allergic reaction to the drug cannot be predicted beforehand. In event of an allergic reaction, the drug will be stopped immediately, and symptoms will be managed appropriately depending on the severity of the reaction.

No single agent has yet been approved by the FDA for GVHD prevention or therapy.³⁴ Contact lenses, commonly used to treat oGVHD, will be withheld during the 14 day wash-out period and over the entire course of the study. Stopping contact lens wear may increase the subject's risk of worsening oGVHD. All study subjects will be encouraged to contact the research team immediately if they experience worsening of oGVHD.

No psychological, social, legal, or financial risk is expected from participating in the research.

There is always a risk of a loss of confidentiality.

2 Study Objectives

The objective of this study is to establish whether patients with ocular graft-vs.-host disease (oGVHD) are able to tolerate receiving rhDNase I 0.1% eye drops four times a day for eight weeks (primary tolerability objective) and to investigate the preliminary efficacy of rhDNase I 0.1% topical eye drop solution in treating oGVHD (primary efficacy objective).

3 Study Design

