3.2 Primary Study Endpoints

Primary Efficacy End Point: The primary end point is a mean reduction in corneal staining score after 8 weeks of treatment, as measured by Fluorescein and Lissamine dye staining.

Primary Tolerability End Point: The change in the test substance tolerance between Day 1 (post-dose) and at weeks 2, 4, 6 and 8.

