3.3.9 Tolerability End Point: Test Substance Tolerance (Visual Analogue Scale)

Subjects will assess their tolerance to the administration of the test medication (placebo/ study drug), utilizing a Visual Analog Scale (VAS). The VAS is a 100 mm horizontal line with verbal descriptors at either end. The VAS ratings will be completed after administration of the test medication on Day 1 (post-dose), week 2, week 4, week 6 and week 8. Subjects will place a single slash mark across the horizontal line between the end labeled "completely intolerable" (0 mm) and "easily tolerable" (100mm). The VAS rating is as follows:

Please rate the degree of comfort or lack of comfort associated with administering the eye drop by making one slash mark on the line below:

Visual Analogue Scale

On the scale of 0 to 100 seen below, please mark where you would rate your tolerability to administration of the test drug.

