3.4 Safety Endpoints

Safety assessments include Vital Signs, recording of all complications and adverse events, as well as ophthalmic exam findings. All ocular and non-ocular adverse events will be assessed for severity and relationship to the investigational product.

Primary safety endpoint:

• The proportion of subjects at week 8 who were able to successfully complete a full eight weeks of therapy with topical administration four times per day (q.i.d.)

Secondary safety endpoint:

- All adverse events reported, whether deemed related to treatment, or not.
- Clinically significant changes in vital signs or ophthalmic examination from baseline.

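### The treatment-by-time mixed model judged at P<0.05 cannot be fitted to week 8 completion, the primary safety endpoint, and a difference test does not answer the tolerability objective

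*Combined protocol and SAP*

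**What the plan says.** Section 2 (Study Objectives) words the primary tolerability objective, over an eight-week course, as follows: "establish whether patients with ocular graft-vs.-host disease (oGVHD) are able to tolerate receiving rhDNase I 0.1% eye drops four times a day". Two endpoints bear on it:

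- The primary tolerability endpoint (section 3.2): "The change in the test substance tolerance between Day 1 (post-dose) and at weeks 2, 4, 6 and 8". Section 3.3.9 describes the instrument: "The VAS is a 100 mm horizontal line with verbal descriptors at either end". It is rated at five time points.
- The primary safety endpoint (section 3.4): "The proportion of subjects at week 8 who were able to successfully complete a full eight weeks of therapy" at the four-times-daily schedule. This is one binary value per subject.

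Neither endpoint has a target, an acceptable lower bound or a margin. On size, section 7.1 states: "The sample size is based on the primary efficacy end point (corneal RBS score").

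On analysis, section 7.2 states that "we will compare each outcome measure between rhDNase I (study) vs. Vehicle (control) group over time using general linear mixed model" and goes on to name mixed-effects ordinal and multinomial logistic regression for ordinal and nominal variables. Every model carries treatment, time and their interaction. The inferential rule is two-sided P<0.05. No confidence interval is specified, and descriptive statistics are mentioned only as a way to describe the sample before modelling. Safety variables are to be analysed by treatment received, but no separate method is named for them.

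Section 7.3 limits the analysis population to subjects with at least two weeks of treatment and the week 2 visit. Section 8.1 allows subjects who withdraw because of an adverse event to be replaced.

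**The concern.** There are two separate problems.

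The first is technical. The only method in the plan that covers a categorical outcome is a repeated-measures logistic model, and completion is not a repeated measure. An analyst following section 7.2 cannot produce the primary safety result and would have to choose a method later, possibly after seeing the data.

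The second is inferential. The objective asks whether patients can tolerate the drops. A two-sided test of no difference is built to detect a difference, and failing to detect one in a small trial says little. Without a stated interval, a non-significant completion or VAS result leaves the reader unable to see how large an excess of stopping, or how large a loss of comfort, remains compatible with the data.

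**Working it through.** **Inputs.** From the plan: 36 per arm (sections 3.1 and 7.1); for staining, "mean RBS score in ocular GVHD population = 3.1, (ii) sigma (standard deviation) = 2.5", expected treated mean 1.24, alpha 0.05 two-sided, 80% power (section 7.1). The plan gives no completion rate, VAS SD or margin. All such values below are assumptions.

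**1. The plan's own sample size.** Difference = 3.1 - 1.24 = 1.86. Normal approximation: n = 2 × (1.960 + 0.842)² × 2.5² / 1.86² = 28.4, so 29 per arm. The noncentral t calculation gives 29.35, so 30, as stated. Power is 80.9% at 30 and 87.6% at 36 per arm. The sizing is correct for staining but says nothing about completion or the VAS.

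**2. Can the specified model be fitted to completion?** With one week 8 record for each of 72 subjects, the fixed-effect columns are intercept (1), treatment (0/1), time (always 8) and treatment × time (0 or 8). Time is 8 times the intercept and the interaction is 8 times treatment, so the matrix has rank 2 of 4. A subject random intercept is not identified either: with a single binary record, any value of its variance can be offset by the fixed effects. Ordinary logistic regression on treatment alone does fit.

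**3. What a non-significant result leaves open.** Take 29/36 on drug (80.6%) and 34/36 on vehicle (94.4%); difference -13.9 points.
- Chi-square: pooled rate 63/72 = 0.875; SE = √(0.875 × 0.125 × 2/36) = 0.078; z = -1.78; P = 0.075. Fisher P = 0.15.
- Wilson limits: 65.0% to 90.2% and 81.9% to 98.5%.
- Newcombe lower limit: -0.139 - √[(0.806 - 0.650)² + (0.985 - 0.944)²] = -0.30.
- Newcombe upper limit: -0.139 + √[(0.902 - 0.806)² + (0.944 - 0.819)²] = +0.02.

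The result is non-significant by either test, yet compatible with a 30-point loss of completers.

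**4. Power of the difference test** (exact enumeration, 36 per arm, assumed rates):

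| Drug v vehicle | Fisher | Chi-square |
|---|---|---|
| 80% v 95% | 34% | 53% |
| 75% v 90% | 29% | 39% |
| 70% v 85% | 24% | 33% |

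**5. What the drug arm alone can show.** Exact 95% CIs: 34/36 gives 81% to 99%; 30/36 gives 67% to 94%.

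**6. A between-arm margin at this size.** With equal true completion of 95%, 90% or 85%, the chance that the Newcombe interval excludes an assumed 15-point loss is 65%, 51% or 41%. For a 10-point loss it is 35%, 24% or 20%.

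**7. Denominator.** Suppose 36 are dosed, four stop before week 2 and two stop later. Over all dosed, completion is 30/36 = 83%. Over the section 7.3 population it is 30/32 = 94%.

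**8. VAS.** For one time point, the 95% half-width for an arm difference is t(70) × SD × √(2/36) = 1.994 × SD × 0.236. For an assumed SD of 20 to 30 mm, that is 9.4 to 14.1 mm.

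**The case against.** The strongest reply is that section 7.2 puts safety variables in a sentence of their own and introduces the models as a way to assess the effect of treatment. On that reading the plan states no method for completion, rather than one that cannot be fitted. That is a possible reading, but section 7.2 speaks of each outcome measure, and on either reading the primary safety endpoint has no usable analysis. Visit-by-visit on-treatment status would supply a time factor, but it is a different outcome from the one in section 3.4.

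A second reply is that this is a Phase I/II trial, reasonably sized on its efficacy endpoint, and that adverse events, the review after 10 completers (section 8.11) and DSMB review of toxicity (section 9.4.1) also protect subjects. Sizing on staining is indeed not an error, and those safeguards are real. None of them sets a tolerability criterion or analyses completion.

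A reader might also go further than the documents allow:

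- **That the model failure extends to the VAS.** It does not. The VAS is continuous and rated five times, and the linear mixed model fits it.
- **That the plan will treat non-significance as proof of tolerability.** No section says so. The fault is that nothing in the plan prevents that reading.
- **That complete corneal clearance fails in the same way because every eye is uncleared on Day 1.** Section 4.1 admits corneal or conjunctival staining, so a target eye can have a clear cornea at entry, and section 3.3 defines clearance only after treatment.

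**Conclusion.** The point holds for the wording of the plan. The section 7.2 model cannot be fitted to the primary safety endpoint; this follows from the endpoint's definition and needs no assumption. A difference test at P<0.05 also does not answer the tolerability objective. Under assumed 15-point drops in completion, its power is between 24% and 53%, depending on the rates and the test, and a non-significant result can be compatible with a 30-point loss. These figures rest on 36 analysed subjects per arm and on assumed rates.

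A reader might infer that the trial itself cannot establish tolerability. That is not supported: 34 completers of 36 on drug would put the exact lower limit at 81%, a usable statement at the present size. What is missing is the analysis, not the data. Nor does the finding call for a non-inferiority test between arms, which an equally tolerated drug would often fail here.

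**What to change.** In section 7.2:

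1. Exempt week 8 completion from the mixed-model and P<0.05 rule. Report each arm's proportion with an exact 95% CI, and the arm difference with a Newcombe or Miettinen-Nurminen 95% CI.
2. Define the denominator as all randomised and dosed subjects, not the section 7.3 subset. Keep any subject replaced under section 8.1 in that denominator.
3. Keep the linear mixed model for the VAS change, and report the arm difference with its 95% CI.
4. State that a non-significant difference in either endpoint will not be read as evidence of tolerability.
5. If a formal conclusion that the drops are tolerated is wanted, set a lower bound for completion in the drug arm, chosen and justified by the investigators before unmasking. This suits the sample size better than a between-arm margin.

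The cost is SAP wording, with no added subjects or visits. The downside is a more cautious tolerability conclusion and, if item 5 is adopted, a bound that the team must defend in advance.
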